#### ***WP1:7.0.4 Short reflection interviews after individual dialysis choice consultation***

Ethnographers will invite patients, and any family members or carers who wish to join, to participate in a short reflection interview (approximately 15 minutes) after the observed dialysis choice consultation. These reflections will take the form of short cognitive interviews [51], incorporating think-aloud techniques. Such reflection interviews will be undertaken with both healthcare professionals (these include renal consultants at renal clearance clinics and specialist pre-dialysis nurses) and patients to investigate both parties' immediate reactions to, and their thoughts and feelings about the appointments. The aim is to generate rich data from small samples, in this case providing evidence about whether home therapy is understood by patients in a consistent way and in the way intended, as well as how well the consultation is meeting its objectives [55].

#### ***WP1:7.0.5 Semi-structured interviews***

Semi-structured interviews will be undertaken with patients, carers/family members and renal unit staff. Interviews will explore in depth how patients have made their treatment choices and their reflections on factors that have helped or hindered treatment choices, including but not limited to home therapy options. Around half of these interviews will be with BME patients and patients from less affluent/socioeconomically deprived backgrounds. Staff interviews will explore in depth how patients are supported to make treatment choices, their reflections on factors that help and hinder treatment choices – particularly for BME and less affluent patients – and what renal units have done to encourage the uptake of home dialysis amongst these groups of patients. Interviews with patients and staff will take place in a private room in the renal centre or will be conducted via telephone, whichever arrangement is more convenient for each interview participant.

#### ***WP1:7.0.6 Secondary data collection***

Written documentary data about the field sites will also be collected, such as unit or organisational policies, strategies, notes of meetings and materials produced for patient counselling and education [56].

#### ***WP1:7.1 Participant identification, recruitment and consent***

Non-participant observation: General observation of: discussions on acute wards about treatment choice; observation in waiting rooms for appointments; open days or group meetings about treatment options and multi-disciplinary team meetings. A formal participant identification and recruitment process will not be undertaken for this strand of data collection, and no identifiable patient information will be collected.

Non-participant observation of one-to-one appointments: Patients and staff members will always be briefed with a participant information sheet and consent form about the presence of the ethnographer

and if they do not wish their one-to-one appointment to be observed (where relevant), they will be able to opt out of this.

Non-participant observation of day to day site activity will be undertaken remotely in instances where relevant meetings or patient education are being delivered virtually. Researchers will join secure remote sessions as observers and participant information and consent processes will follow the protocol for non-participant observation. Researchers can also obtain participant consent by telephone in accordance with study specific telephone guidance. No identifiable patient information will be collected.

Short reflection interviews: These will be think-aloud interviews with nurses and patients (n=6-8 encounters per site; n=24-32 in total). These will be conducted immediately after the healthcare professional appointments. Consent for these reflection interviews will be taken face-to-face from both patient and staff participants straight after each appointment which is the subject of the think-aloud interview. Think-aloud interviews will be audio-recorded using encrypted digital recorders and recordings kept on a secure network drive on University of Birmingham premises before being independently transcribed.

Semi-structured interviews (patients and carers/family members): Semi-structured interviews will be undertaken with 10-12 patients per site (n=40-48 in total), and with 5 carers/family members per site (n=20 in total). Lists of potentially eligible patients will be produced and screened against the inclusion/exclusion criteria by renal unit staff every other month. In order to determine socioeconomic status, home residence postcodes will be converted to a deprivation quartile on the Index of Multiple Deprivation using the online tool Geoconvert (<http://geoconvert.mimas.ac.uk>).

Postcodes will only be linked to identifiable patient/carer names after permission from the patient/carer has been given to share these details with the research team. The postcode will be stored securely at the University of Birmingham.

Where feasible, a maximum variation sampling frame will be used, to ensure diversity in terms of ethnicity, disadvantage, age, gender and comorbidities, and to include patients who have been through the whole treatment decision-making process as well as those who may only have seen the consultant in a low-clearance clinic.

Patients who match the inclusion criteria will initially be informed about the research by the delegated local site staff, be invited to participate by letter and given a copy of the participant information sheet. Local site staff will provide one reminder phone call in the event of non-response after 1 week.

Patients who have expressed an interest and agreed that their contact details can be shared with the research team will receive a follow up telephone call from a member of the research team to arrange for consent to be obtained and to set up a time and date for the interview.

Patients who wish to participate in a semi-structured interview can be interviewed at the renal unit at their next appointment, with written consent taken at that time by the researcher. Alternatively, interviews can take place by telephone following receipt of a consent form completed and signed by

the participant. Researchers can also obtain participant consent by telephone in accordance with study specific telephone guidance.

For carers/family members, written information about the study and a consent form will be included in the pack sent to the patient, with an invitation to pass these on to their carer or a relevant family member if they would also like to be interviewed.

Interviews will be audio-recorded using an encrypted digital recorder and kept on a secure network drive on University of Birmingham premises before being independently transcribed.

**Semi-structured interviews (staff):** Semi-structured, interviews will be undertaken with 12-14 staff per site (n=48-56 in total). A staff representative (or R&D staff member) from the local participating site will be delegated the duty of identifying participants and will make the initial approach to these participants, to determine their willingness to be contacted by a member of the study team who will provide further information about the study and undertake consent procedures. A maximum variation sampling frame will be used, to ensure that the perspectives of different staff groups are included. Interviewees will therefore include doctors (consultants, registrars) nurses (specialist home therapy staff, pre-dialysis nurses, ward staff, dialysis units), allied health professionals (dietitian, psychologist/counsellor) clinical lead, and business managers. Interviews will be audio-recorded using an encrypted digital recorder and kept on a secure network drive on University of Birmingham premises, before being independently transcribed.

For semi-structured qualitative interviews with staff, patients and carers all interviewees will be offered the opportunity to undertake their interview via video-conferencing (MSTeams or Zoom, University of Birmingham enhanced security accounts) if this is preferred to a telephone interview. This may enhance rapport by giving a face-to-face feel to the interviews in instances where in person interviews are restricted. These interviews will follow the same participant information and consent processes as the telephone interviews .

## **WP1:8 QUALITATIVE DATA ANALYSIS**

### ***WP1:8.1 Documentary analysis***

Analysis of each site's written documents will use conventional content analysis [57] and be undertaken contemporaneously with the ethnographic data collection, so that issues identified from the documentary analysis can be explored further in interviews.

### ***WP1:8.2 Non-participant observations***

Data will be collected in the form of field notes of observations. These will be shared via a secure team drive and weekly debriefing meetings will ensure progress, meeting milestones and an iterative data analysis process. No identifiable data will be collected in the observation process.

### **WP1:8.3 Interviews**

Patient, staff and carer/family member interviews, including both the reflection interviews conducted immediately after the consultation and the longer semi-structured interviews, will be transcribed verbatim by a professional transcription company and checked against recordings for accuracy.

### **WP1:8.3 Data synthesis and analysis**

Observational data, ethnographers' field notes and interview transcripts will be imported into the qualitative data-analysis software QSR NVivo 12 for inductive thematic analysis [61]. Each site's data will be analysed separately to capture distinctive centre effects. Two researchers will generate an initial coding framework and fields using a broadly representative sample of 10% of each type of data. Results will be reviewed by the team and adjusted to produce a codebook and coding framework. The analytical approach will be inductive, based on iterative data coding and comparison.

Analysis will be guided by the aim of identifying the specific approaches of units and understanding how different approaches are perceived and acted on by patients. Where data do not fit with existing themes, new themes will be developed or existing ones revised until all the data can be assigned to themes. Data from staff and patients will initially be analysed separately. Data from patients, carers and staff will be combined with the documentary analysis to build up a detailed picture of each site. Themes will then be mapped to the NASSS framework in order to identify the main factors which influence the uptake of home therapies, and how these factors interact. A second stage of analysis will look across the four sites' ethnographies to characterise the centre effect and identify promising practices that can be explored in the subsequent national survey.

## **WP1:9 DATA HANDLING**

The research team will preserve the confidentiality of participants in accordance with the Data Protection Act 1998 and any subsequent data protection laws that supersede it (such as the General Practice Data Protection Regulations (GDPR) 2018). Patients and staff participating in the semi-structured or think-aloud interviews will be assigned a unique identifier (as will carers/family members participating in semi-structured interviews) that links them to the relevant case study site, and all data will be anonymised. All participants will be assured of the confidentiality of the data collected, and will be asked for permission to publish anonymised quotations from their interviews in research outputs.

Field notes and data collected from ethnographic non-participant observation will be kept securely on University of Birmingham premises, on a secure network drive to which only the immediate members of the research team will have access. Interview data will be collected using encrypted recording devices, with audio files securely stored on University of Birmingham network servers. For the purposes of interview transcription, an independent, university-approved transcription company (Clayton Research Support) will be used to which audio files will be securely uploaded. A confidentiality agreement will be signed prior to this work commencing. Interview transcripts will be password protected and also stored on University of Birmingham network servers. Any paper files (such as consent forms) will contain no identifiable data, and will be stored in locked filing cabinets in a

locked office in an area of the Institute of Applied Health Research, University of Birmingham which can be accessed only by swipe card and numerical keycode.

### **WP1:9.5 Archiving**

As per the University of Birmingham's regulations on the retention of research data, anonymised, analysed data will be retained for ten years, and will be securely archived on University of Birmingham premises, with the local PI as data custodian. At the end of the study, with participants' consent, data in the form of anonymised transcribed interviews will be stored in the University of Birmingham Data repository and will be made available to bona fide researchers on request. This process is managed by the University of Birmingham Research Governance Office.

The local participating site is required to archive essential study documents in accordance with local Trust procedures, for 10 years after the 'End of study Declaration' (Date of end of study submission to Regulatory bodies).

## **WORK PACKAGE 2 (WP2): GRAPHICAL MARKOV AND MULTISTATE MODELLING BASED ON LINKED RENAL UNIT SURVEY AND UK RENAL REGISTRY DATA**

### **WP2: RATIONALE**

The findings from WP1 will inform the development of a quantitative national survey of all dialysis units in England (n=52), to identify local patterns of practice, explore explanations behind home therapy uptake rates, and to establish the influence of commissioning strategies. The survey will also include questions that are informed by an up to date rapid literature review. By linking the survey findings to actual outcome data obtained from the renal registry it will be possible to quantify how different factors influence the variation in use of home therapies in the context of competing treatments as well as linking these to clinical outcomes.

### **WP2: SURVEY DESIGN**

Survey design will be based on the literature on known factors influencing home therapy uptake along with the findings from the ethnographic observations and semi-structured patient and practitioner interviews from WP1. WP1 will identify specific approaches of renal units towards supporting patients to make treatment choices, characterise the potentially modifiable components of the centre effect in home therapy uptake, and identify examples of best or promising practice that may work to reduce or eliminate the centre effect. These findings will be used to develop the survey (i.e. qualitative insights converted into semi-quantifiable survey questions), through regular and iterative team meetings, initially within WP1 (up to 9 months) and then for 3 months in WP2.

The survey will take around 20 minutes to complete and will consist – where feasible – of short questions with tick-box style or Likert scale responses, with the option of additional free text responses, in order to maximise response rates and ensure comparability of responses across renal units.

## **WP2: Survey content**

Although the content of the survey cannot be specified in advance of undertaking the ethnographic work, survey questions are likely to cover policy/commissioning issues that may impact on home therapy uptake, issues related to financial considerations, renal unit organisation and practice, the influence of unit leadership, renal unit culture around home therapies, and patient-specific factors. Key lines of enquiry will include but not be limited to:

- The principles underpinning home therapy service provision and whether patients from specific groups are prioritised when offering home treatment options
- What treatment options are provided and the criteria for accessing them
- How renal units respond to diverse population needs or unmet needs, particularly amongst patients from BME and socioeconomically deprived communities
- Factors influencing the pattern of home therapy provision
- Examples of innovative practice, use of new HHD technologies, models of assisted care delivery
- Respondent perceptions about the existence of a home therapies centre effect and the factors associated with it
- When and how patient-practitioner discussions about home therapies occur
- The potential impact of innovations such as incentivisation of home therapies
- The influence of tariff structures on home therapy provision and uptake
- The role of renal unit leadership, hierarchy and management in affecting home therapy uptake

## **WP2:6 ELIGIBILITY CRITERIA**

All renal dialysis units in England (n=52) will be invited to participate in the national survey.

## **WP2:7 STUDY PROCEDURES**

The survey will be created by, and administered using the Online Surveys tool (formerly Bristol Online Surveys), for which University of Birmingham holds an institutional licence. Surveys will be made available to potential participants electronically, via a web link embedded in a brief invitation email. Online Surveys was chosen as the survey platform because it is designed to protect respondent anonymity - the system does not use cookies for survey completion, and information about respondents' IP address cannot be accessed. Survey respondents will be able to take part in the survey in any location, at a time of their choosing, minimising any potential inconvenience of participation in the research. The Online Survey allows participants to save their answers when partway through the survey and return to it later for completion at any point

The survey will be piloted for relevance and readability in the West Midlands with 2-3 renal unit staff who will not be invited subsequently to complete the survey when disseminated, and by the project PPIE representatives.

### ***WP2:7.1 Recruitment***

The clinical lead of each dialysis unit across England will be sent a covering email explaining the study and an electronic link to the survey, which will be administered using the secure JISC Online Survey tool (formerly known as Bristol Online Surveys), for which University of Birmingham has an institutional license. Clinical leads will be asked to forward the survey link to key staff within their unit (managers, lead clinicians, nurses, healthcare assistants (HCAs), allied health professionals (AHPs), finance officers), with the aim of obtaining at least 8 responses per renal unit. The survey link will also be sent to commissioners of renal services, who will be identified and approached by the study team member representing NHS England.

The reason for including more than one respondent per centre is to get a range of expertise and thus improved accuracy and completeness of the responses. The questionnaire will be designed such that there will be overlap in the questions answered by team members: for example, the director of the home therapies team will be asked to report on their perception of how financial factors influence clinical practice, while the directorate finance manager will have a more technical understanding of any questions in this domain, but will not be expected to answer clinical questions which are clearly outside their expertise. This will allow us to obtain more detail and test the internal validity of the survey, and where disagreement is identified, to identify potential mechanisms and associated intervention targets for exploration in subsequent work packages.

### ***WP2:7.2 Consent***

There will be no formal consent process for the survey – return of the survey will be taken as consent to participate. The front page of the survey will include a tick box for respondents to acknowledge a statement assuring them of the confidential handling of any information they provide in their response. With respect to patient data obtained from the registry, this is not required as the UK Renal Registry has Section 251 approval for research using pseudonymised routinely collected patient data. The agreed process requires an application which is reviewed by the data release group.

## **WP2:8 STATISTICS AND DATA ANALYSIS**

### ***WP2:8.1 Sample size calculation***

There is no formal sample size calculation for the national survey as this is not a sample, but a whole country study. The sample size is determined by the number of centres from which we obtain information through the survey, rather than the number of survey respondents per renal unit, which will determine the expertise with which it is completed and thus the accuracy of the information. With approximately 8 responses planned per renal unit, we would expect up to 400 completed surveys to be returned. The total number of patient-level observations is estimated to be around 27,000 and will depend on the number of patients on renal replacement therapy.

### ***WP2:8.2 Planned recruitment strategy***

We aim to obtain up to 400 completed surveys over a period of 8 weeks. Several strategies will be used to maximise response rates: endorsement of the survey will be sought via the Renal Association Clinical Directors Forum; reminder emails will be sent to clinical leads by the Birmingham research team 2-3 weeks after initial survey dissemination; up to three follow-up telephone calls will target non-responding or under-represented renal units, and the survey will be publicised via professional networks. Monitoring of the renal unit staff groups returning surveys will be undertaken on an ongoing basis. This will allow us to target under-represented groups with new invitations at the 2-3 week reminder point, as well as reminding non-respondents who have already received the survey to return it. Survey recipients receiving a reminder will have a further 5-6 weeks to respond. Newly-invited survey recipients will receive reminders after 2-3 weeks and will also have an 8-week period during which the survey is open to them. Additionally, although survey responses will be anonymous, respondents will have the option to provide some contact details in order to receive a £25 voucher to reimburse their time spent completing the survey.

### ***WP2:8.3 Statistical analysis plan***

Surveys will first be analysed descriptively to map patterns of home therapy service provision across the country, and to identify differences and commonalities in renal unit practice. Respondents' views on service provision, possible improvements and commissioning will also be analysed descriptively, looking for differences and commonalities across stakeholder group (e.g. clinical leads, commissioners) and to provide a preliminary understanding of the relative contribution of different factors (leadership, culture etc.) to the home dialysis centre effect. This analysis will also identify key issues for further exploration in the health economic analysis (WP3). Following linkage of the survey data to the UK Renal Registry patient level data we will undertake the following analyses:

#### ***WP2:8.3.1 Summary of baseline data and flow of patients***

The individual demographic and clinical characteristics from the linked survey and Renal Registry cohort will be described using frequencies and percentages for categorical data and median and interquartile range for continuous data. A flow chart of patients included in the analysis will also be presented.

#### ***WP2:8.3.2 Primary Outcome: graphical Markov modelling of factors that explain the variation in home dialysis uptake***

We will employ sequences of regressions [53-64] coupled with a causal graph to define a graphical Markov model that extends path analysis to formulate an explanatory model for home dialysis uptake. The model is formulated by ordering the variables in groups of primary outcomes (e.g. HD uptake), potential intermediary variables (e.g. dialysis unit practices, centre characteristics, policy and commissioning, patient comorbidities) and background variables (Fig 1). The model is developed by fitting ordered sequences of linear or logistic regression models and the strength of associations is

quantified through partial correlation coefficients, with variables located on the left taken as response variables to those located to the right of them in a postulated ordering. The choice and ordering of the variables will be informed by the literature review and the ethnographic study. The associations between two variables in the model can be direct or indirect; for example, a dialysis unit characteristic (e.g. whether it is also a transplant centre) may affect home dialysis use directly or indirectly due to a unit practice identified by the survey. Importantly, it is possible to assess interactions or whether any association holds in the same direction and at the same magnitude for different patient demographics, e.g. ethnicity or socio-economic status.

[figure not shown]

[figure not shown]
Figure 1: Example of postulated order of sequences of regressions model variables. Variables located on the right are regarded as explanatory to those located to their left. The associations between two variables in different boxes can be direct or indirect through intermediary variables. SES: Socio-economic status

The strength of this approach is that it provides a framework to identify potential causal relationships amongst many patient- and practice-related factors, and their impact on HD uptake, thereby offering a powerful tool to deal with the complexity likely to be identified by the ethnographic study. The main outcomes of this approach include (1) a causal graph that displays pathways of associations starting from demographic factors through intermediary factors, leading to home uptake, indicated by series of variables connected by arrows or lines, including a measure of relative importance – this will help present and greatly simplify the synthesis of findings (WP4); and (2) an interpretation based on graph theory and probabilistic theory to explore the relationship between selected subsets of variables and thus enable the assessment of competing hypotheses. This will provide a robust mechanism for the choice of the most important modifiable and cost-effective factors when developing the intervention (WP5).

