### **WP2:8.3.3 Secondary Outcome Analysis: Multistate modelling of Patient level treatment modality history and mortality**

The results from the graphical Markov model will inform the development of a multi-state model,[66] for patients requiring renal replacement therapy. This will estimate the rates of: home and in-centre dialysis uptake, transplantation, transitions from one modality to another, and death (Fig. 2). The model will quantify the impact of changing centre patterns, identified by the graphical Markov model, on the rates of home dialysis usage. The transition rates will include random intercepts at the centre-

level to account for heterogeneity among dialysis units. The estimated parameters of this model will inform the health economic analysis (WP3).

*Figure 2. Multi-state model to estimate the rates of home dialysis usage combined, similar models will be built replacing home dialysis by two states for PD and HHD separately allowing transitions between these states*

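### The primary graphical Markov model names no term for centre, so as written its standard errors for unit-level practices are too small, by roughly 1.4 to 6 times

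*Protocol*

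**What the plan says.** WP2:8.3.2 gives the model class for the primary analysis: "The model is developed by fitting ordered sequences of linear or logistic regression models". Home dialysis uptake is the primary outcome. The next block holds "potential intermediary variables (e.g. dialysis unit practices, centre characteristics, policy and commissioning, patient comorbidities", so variables with one value per unit sit beside variables that differ between patients. Each variable is treated as a response to those on its right in the postulated order, and the strength of association is "quantified through partial correlation coefficients". No random effect, clustered variance or other centre term is named here, under adjusted analysis (WP2:8.5) or under missing data (WP2:8.8). The last of these says only that all models are fitted by maximum likelihood.

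The secondary analysis is different. In WP2:8.3.3, "The transition rates will include random intercepts" for centre, and heterogeneity among units is given as the reason.

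WP2:8.1 says: "There is no formal sample size calculation for the national survey as this is not a sample, but a whole country study". It continues: "The sample size is determined by the number of centres from which we obtain information through the survey". It also says: "The total number of patient-level observations is estimated to be around 27,000". WP2:6 fixes the number of units: "All renal dialysis units in England (n=52) will be invited to participate in the national survey".

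**The concern.** Patients in one unit share that unit's practices and whatever else drives its uptake. A practice with one value per unit is therefore observed at most 52 times, however many patients are in the file. A regression on patient rows without a centre term counts each patient as independent evidence about the practice and understates its standard error.

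The study exists to make inferences about such practices. According to WP2:8.3.2, the resulting graph, with its measure of relative importance, guides the choice of modifiable factors for the intervention. WP5:7.1 draws a list of 6–10 factors from WP1 and WP2 together, and WP2:8.3.3 says the results inform the multistate model, whose parameters go to the economic analysis. A practice kept in the graph because its error bar is too narrow would be carried into all of these.

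The ordering raises a second question. Unit practices can themselves be responses to variables on their right, and the protocol does not say whether those regressions use one row per unit or one row per patient.

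**Working it through.** The protocol states no power, alpha or intracluster correlation (ICC) for this analysis, so there is no figure of its own to reproduce. The check uses its other numbers.

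**Inputs from the protocol**
- About 27,000 patient-level observations (WP2:8.1).
- 52 units (WP2:6).
- Centre ranges in section 1.1: PD at initiation 6.3% to 49.7%; prevalent home therapy 6% to 27%.

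**Assumptions**
- Centre effects are normal on the logit scale.
- Tests are two-sided at 5%.
- The centre extremes are taken at face value, although they include some sampling noise.

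**Step 1: cluster size.** m = 27,000/52 = 519.

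**Step 2: between-centre spread.** The expected range of 52 standard normal values is 4.53.
- PD at initiation: (logit 0.497 − logit 0.063)/4.53 = (−0.012 + 2.700)/4.53 = 0.59.
- Prevalent home therapy: (logit 0.27 − logit 0.06)/4.53 = (−0.995 + 2.752)/4.53 = 0.39.

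On the proportion scale these logit SDs give ICCs of about 0.056 and 0.018.

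**Step 3: effect on a unit-level covariate.** Design effect DE = 1 + (m − 1) × ICC. The standard error is too small by a factor √DE. The true error rate of a nominal 5% test is 2 × [1 − Φ(1.96/√DE)]. The model adjusts for other variables, so the lower rows shrink the ICC in proportion to the centre variance left unexplained.

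| Centre variance explained by covariates | ICC | DE | SE too small by | Null practice flagged |
|---|---|---|---|---|
| none, prevalence range | 0.018 | 10.3 | 3.2 | 54% |
| none, PD initiation range | 0.056 | 30.0 | 5.5 | 72% |
| 75%, prevalence range | 0.0045 | 3.3 | 1.8 | 28% |
| 75%, PD initiation range | 0.014 | 8.3 | 2.9 | 50% |
| 90%, prevalence range | 0.0018 | 1.9 | 1.4 | 16% |
| 90%, PD initiation range | 0.0056 | 3.9 | 2.0 | 32% |

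With no variance explained, the effective number of observations behind a unit-level practice is 27,000/30.0 = about 900 to 27,000/10.3 = about 2,600.

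**Step 4: check by simulation.** There were 1,000 runs per scenario with 52 units of unequal size, about 27,000 patients, and a practice with no effect present in 26 units.

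| Centre variance explained | Range used | SE ratio | Flagged, no centre term | Flagged, centre-clustered SE (50 df) |
|---|---|---|---|---|
| none | PD initiation | 6.0 | 73% | 5.6% |
| 75% | PD initiation | 3.2 | 58% | 6.8% |
| 90% | PD initiation | 2.2 | 39% | 5.7% |
| none | prevalence | 3.5 | 59% | 5.9% |
| 75% | prevalence | 2.0 | 34% | 6.0% |
| 90% | prevalence | 1.5 | 19% | 5.8% |

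The simulated ratios are a little above the formula, as unequal unit sizes would lead one to expect. The two methods together give the quoted ranges.

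**The case against.** The strongest reply is that the protocol never says the regressions are single-level. A random-intercept logistic model is still a logistic regression, and a separate analysis plan could add the centre term. This stands to a degree: the absence of a centre term is read from the specification and is not declared as a decision. But the text sits under the protocol's own heading for the statistical analysis plan, it names the model class, and the next subsection names centre intercepts for the secondary model. Nothing in the document supplies the term for the primary one.

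Second, the protocol gives no alpha and no rule for keeping an arrow; strength is a partial correlation. This stands too, so the false-positive rates are conditional on an assumed 5% test. Arrows must still be kept or dropped somehow, and any rule that uses the standard error inherits the problem.

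Third, there are later safeguards: the multistate model has centre intercepts, and factor selection also draws on ethnography, literature and workshops. These lessen the downstream risk. They do not undo a screening step already made on wrong error bars.

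A reader might also infer three stronger things that the document does not support:
- That most arrows from unit practices would be spurious. A rate per null practice does not give that share, which also depends on how many practices are truly null and on power.
- That unit-level responses will be fitted on patient rows. The row structure is not stated, and the remark that centres set the sample size fits a centre-level analysis equally well. No error rate is offered for this part.
- That the top of the range, about 6 times and 73%, is the expected size. It uses the PD-initiation extremes with no centre variance explained.

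**Conclusion.** The concern holds. The primary model, as specified, has no term for centre, and if followed it gives standard errors that are too small for the unit-level practices the study is designed to assess. The understatement is about 3 to 6 times before covariates explain centre variance and about 1.4 to 3 times if they explain 75–90% of it. The matching chance of flagging a null practice is roughly 16–73%.

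These sizes rest on ICCs inferred from extreme centre values, on all 27,000 observations entering the model, and on an assumed two-sided 5% test. Patient-level covariates that vary mainly within units are much less affected. The problem lies in the error bars and what is selected from them; ignoring clustering does not by itself show that the point estimates are biased. It should be settled before the linked data are analysed, because this is the primary analysis and the protocol already accepts the need for a centre term in the secondary one.

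**What to change.** Amend WP2:8.3.2 to state:

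1. Every regression with a patient-level response includes a centre random intercept, or uses centre-clustered standard errors suited to about 52 clusters. A separate fixed effect for each centre is not a substitute, because it would absorb every variable with one value per unit.
2. Every regression with a unit-level response is fitted at centre level, on up to 52 rows, with patient mix entered as centre summaries.
3. The between-centre variance in uptake is reported before and after the unit-level factors are added, with the same patient-level covariates in both fits. The section heading asks which factors explain the variation, and this answers it directly. It needs the random-intercept model even if clustered standard errors are used elsewhere.

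The cost is a few sentences and modest programming, with no new data. The downside is real: intervals for unit-level factors will be wider and fewer of their arrows will be kept. That reflects the information 52 units can give.
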